12.4 Protocol Adherence and Deviations

The study will be conducted as described in this protocol. Investigators are not permitted to deviate from this protocol except to protect patient rights, safety or well-being. Any deviations from this protocol must be documented by the Investigator. If an emergency situation arises in which the rights, safety and well-being of a subject may require immediate alternative intervention, the Investigator should act in the best interest of the subject. Sponsor and the site's IRB must be notified immediately if this occurs. This should be followed with written confirmation that describes the emergency action and outcomes, to Sponsor and per IRB reporting requirements. Protocol deviations will be reviewed during routine monitoring visits. Investigators will be required to identify preventive and corrective actions to prevent further deviations. An Investigator may be disqualified from the study for repeated and/or egregious protocol deviations.

This protocol may be amended as necessary by the Sponsor. Any protocol amendments will be documented via an incremented version of this protocol (with relevant revision history) and a “was/is” comparison table to highlight the protocol changes. Amendments to the protocol must undergo the same approval process by the Sponsor, Investigators, IRBs and regulatory authorities as the original protocol.

12.5 Device Accountability

Only commercially available Phasix™ ST mesh will be used. Device accountability will not be required.

12.6 Data Collection

The Investigator is responsible for completely and accurately recording study data in the appropriate sections of the eCRFs provided by Sponsor. The eCRFs must be signed by the Investigator or by his/her documented designee.

The Investigator is also responsible for making source documents and forms readily available for a thorough review by the study monitor at each monitoring visit. The monitor will ensure the accuracy of data recording at each investigational site by comparison to supporting source documents during periodic site visits. Adherence to proper recording of information as well as assuring that corrections are being made will also be addressed during these periodic visits.

12.7 Subject Compensation

To compensate subjects for their time and participation, they may receive stipends upon completion of each of the protocol specified study visits. If the subject does not complete a visit, they will not be compensated for that visit.

12.8 Communications with the Sponsor

Although the Investigator and his/her staff may have contact with other key individuals at the Sponsor throughout the course of the study, all communications regarding conduct of the study must be channeled through the Sponsor’s clinical affairs personnel or their designees.

12.9 Required Documentation

An Investigator may not screen or enroll subjects until authorized to do so by the Sponsor. At a minimum, the following documentation must be received by the Sponsor prior to study commencement:

- CVs and medical licenses for the principal Investigator and sub-Investigators;

- Signed Clinical Study Agreement;
- Signed Nondisclosure Agreement;
- Signed “Protocol Signature Page” (page ii of this protocol);
- Written approval from the IRB of both the protocol and ICF;
- Signed Financial Disclosure Statement; and
- IRB Assurance of Compliance Form or equivalent.

13 SITE MONITORING

The study monitors are designated as agents of the Sponsor and are assigned to oversee the conduct and progress of the study and to be the principal communication link between the Sponsor and the Investigator.

The study monitors will be involved in Investigator selection and training, assurance of IRB approvals, and periodic on-site inspection and monitoring of sites and records, to ensure continued compliance with the protocol and adequacy of the Investigator and the facility to carry out the study. In addition, the monitor will verify that the device is being used in accordance with the protocol instructions.

The site may also be subject to a quality assurance audit by personnel of the Sponsor as well as by FDA representatives.

The monitor will perform several types of site visits during the course of the study. In all cases, the study monitor will provide a written summary of the visit, including necessary follow-up items, to the Investigator and Sponsor.

It is important that the Investigator(s) and the relevant site personnel are available during the monitoring visits, and possible audit, and that sufficient time is devoted to the process.

13.1 Study Initiation Visit

Before the study begins, the study monitor will visit the site. The purpose of this visit is to review with the Investigator and staff the provisions and proper conduct of the clinical evaluation. This includes a detailed review of the protocol and eCRFs with instructions as to their completion, as well as reviewing regulations pertaining to the conduct of the clinical study. Arrangement for timely and accurate reporting of clinical data and relevant medical events will be established as well as ensuring safe and secure storage for the study devices.

The study monitor will:

- Confirm that the ICF to be used is the one approved by the IRB;
- Verify that all necessary documents are on file at the site; and
- Confirm that there are provisions to continue and maintain all documents and records throughout the study as required by GCP regulations.

13.2 Ongoing Monitoring Visits

The study monitor will maintain personal contact with the Investigator and staff throughout the study by telephone, e-mail, fax, mail, and on-site visits. On-site monitoring will begin after the first subjects are enrolled and continue until the study is completed. The monitoring will assure continued protocol compliance, adequate subject enrollment, accurate data reporting (including the comparison of eCRFs with subject records), device accountability (if required), and continued IRB acceptance of the study. The study monitor will evaluate and summarize the results of each visit in written reports, identifying any ongoing data problems with any study site and specifying recommendations for resolution of noted deficiencies. A formal monitoring plan will describe the planned extent of source data verification.

13.3 Final Monitoring Visit

At the completion of the study, the study monitor will conduct a final on-site visit. The purpose of this visit is to collect all outstanding study data documents, confirm that the Investigator's files are accurate and complete, review the record retention requirements with the Investigator, provide the return of unused devices (if required) to the sponsor, review records which account for device shipment (if required), and assure that all applicable requirements for closure of the study are met. The actions and observations made at this visit will be recorded and filed.

14 TERMINATION OF STUDY

Sponsor reserves the right to suspend enrollment or terminate the study at any time as set forth in the Clinical Study Agreement. Written notice will be submitted to the Investigator in advance of such termination.

Sponsor may suspend enrollment or terminate the study at a specific site for reasons including, but not limited to, inadequate data collection, low subject enrollment rate, achievement of the total enrollment, or non-compliance with the protocol or other clinical research requirements.

15 REPORTING REQUIREMENTS

The Investigator must promptly report to Sponsor any withdrawal of IRB approval at the site. Additional reporting requirements of the Investigator include:

- Reporting all ICF violations to the IRB
- Reporting all device related AEs to Davol Field Assurance Department
- Reporting all SAE to the Davol Clinical Team

16 RECORD RETENTION

The investigator shall retain all study records for a period of 2 years after the investigation is terminated or completed, or until the records are no longer required as determined by the Sponsor. The investigator may withdraw from the responsibility to maintain records for the period required and transfer custody of the records to any other person who will accept responsibility for retaining them with pre-approval. Notice of a transfer shall be given to the Sponsor not later than 10 working days after transfer occurs.

Appendix 2: Surgical Site Infection Classification²⁴

Superficial Incisional Surgical Site Infections (SSI)

Infection occurs within 30 days after the operative procedure (where day 1 = procedure day)

AND

involves only the skin or subcutaneous tissue of the incision

AND

at least one of the following:

- A. Purulent drainage from the superficial incision or subcutaneous tissue.
- B. Organisms isolated from an aseptically obtained culture of fluid or tissue from the superficial incision.
- C. Superficial incision that is deliberately opened by a surgeon, attending physician or other designee and is culture positive or not cultured
AND
Patient has at least one of the following signs or symptoms: pain or tenderness; localized swelling; erythema; or heat. A culture negative finding does not meet this criterion.
- D. Diagnosis of a superficial incisional SSI by the surgeon or attending physician or other designee.

COMMENT: There are two specific types of superficial incisional SSIs:

1. Superficial Incisional Primary (SIP) –a superficial incisional SSI that is identified in the primary incision in a patient that has had an operation with one or more incisions (e.g., C -section incision or chest incision for CBGB)
2. Superficial Incisional Secondary (SIS) – a superficial incisional SSI that is identified in the secondary incision in a patient that has had an operation with more than one incision (e.g., donor site incision for CBGB)

The following do not qualify as criteria for meeting the definition of superficial SSI:

- Diagnosis/treatment of cellulitis (redness/warmth/swelling), by itself, does not meet criterion d for superficial incisional SSI. An incision that is draining or culture (+) is not considered a cellulitis.
- A stitch abscess alone (minimal inflammation and discharge confined to the points of suture penetration).

Deep Incisional SSI

Infection occurs within 90 days after the operative procedure (for herniorrhaphy)(where day 1 = procedure day)

AND

involves deep soft tissues of the incision (e.g., fascia and muscle layers)

AND

patient has at least one of the following:

- a. Purulent drainage from the deep incision.

b. A deep incision spontaneously dehisces or is deliberately opened or aspirated by a surgeon, attending physician or other designee and is culture positive or not cultured
AND
patient has at least **one** of the following signs or symptoms: fever ($>38^{\circ}\text{C}$), localized pain or tenderness. A culture negative finding does not meet this criterion.

c. An abscess or other evidence of infection involving the deep incision that is detected on gross anatomical or histopathologic exam, or imaging test.

COMMENTS: There are two specific types of deep incisional SSIs:

1. Deep Incisional Primary (DIP) –a deep incisional SSI that is identified in a primary incision in a patient that has had an operation with one or more incisions (e.g., C-section incision or chest incision for CBGB)
2. Deep Incisional Secondary (DIS) – a deep incisional SSI that is identified in the secondary incision in a patient that has had an operation with more than one incision (e.g., donor site incision for CBGB)

Organ/Space SSI

Must meet the following criteria:

Infection occurs within 90 days after the operative procedure (for herniorrhaphy)(where day 1 = procedure day)

AND

infection involves any part of the body deeper than the fascial/muscle layers, that is opened or manipulated during the operative procedure

AND

patient has at least **one** of the following:

- a. purulent drainage from a drain that is placed into the organ/space (e.g., closed suction drainage system, open drain, T-tube drain, CT guided drainage)
- b. organisms isolated from an aseptically-obtained culture of fluid or tissue in the organ/space
- c. an abscess or other evidence of infection involving the organ/space that is detected on gross anatomical or histopathologic exam, or imaging test

AND

meets at least **one** of the organ/space infection site “intraabdominal” criteria:

1. Patient has organisms cultured from abscess and/or purulent material from intraabdominal space.
2. Patient has abscess or other evidence of intraabdominal infection on gross anatomic or histopathologic exam.
3. Patient has at least two of the following signs or symptoms: fever ($>38.0^{\circ}\text{C}^{\pm}$), nausea*, vomiting*, abdominal pain*, or jaundice*

And at least one of the following:

- a. organisms seen on culture or Gram stain of drainage or tissue obtained during invasive procedure or from an aseptically-placed drain (e.g., closed suction drainage system, open drain, T-tube drain, CT guided drainage)

- b. organisms cultured from blood and imaging test evidence suggestive of infection (e.g., ultrasound, CT scan, MRI, radiolabel scans [gallium, technetium, etc.] or on abdominal x-ray), which if equivocal is supported by clinical correlation.

* With no other recognized cause

± As documented in the medical record

Appendix 3: Surgical Wound Classification²³

- Class I/Clean: An uninfected operative wound in which no inflammation is encountered and the respiratory, alimentary, genital, or uninfected urinary tract is not entered. In addition, clean wounds are primarily closed and, if necessary, drained with closed drainage. Operative incisional wounds that follow nonpenetrating (blunt) trauma should be included in this category if they meet the criteria.
- Class II/Clean-Contaminated*: An operative wound in which the respiratory, alimentary, genital, or urinary tracts are entered under controlled conditions and without unusual contamination. Specifically, operations involving the biliary tract, appendix, vagina, and oropharynx are included in this category, provided no evidence of infection or major break in technique is encountered.
- Class III/Contaminated*: Open, fresh, accidental wounds. In addition, operations with major breaks in sterile technique (e.g., open cardiac massage) or gross spillage from the gastrointestinal tract, and incisions in which acute, nonpurulent inflammation is encountered including necrotic tissue without evidence of purulent drainage (e.g., dry gangrene) are included in this category.
- Class IV/Dirty-Infected*: Old traumatic wounds with retained devitalized tissue and those that involve existing clinical infection or perforated viscera. This definition suggests that the organisms causing postoperative infection were present in the operative field before the operation.

* NOTE: In this study, subjects with Class II, Class III and Class IV wounds are to be excluded from enrollment.

Appendix 4: Routine Culture²⁵

BASIC GUIDELINES FOR COLLECTION

1. Collect the material from the site in which the etiologic agent will most likely be found.
2. Obtain cultures prior to administration of antibiotics whenever possible.
3. Collect adequate volume of material. Inadequate amounts of specimen may yield false negative results.
4. Collect specimen in a manner that minimizes or eliminates contamination from indigenous flora as possible to ensure that the sample will be representative of the infected site.
5. Use appropriate collection devices, transport media, and sterile, leak proof containers.
6. Use sterile equipment and aseptic technique to collect specimen to prevent introduction of microorganisms during invasive procedures.
7. Clearly label the specimen including specific information regarding site of collection (e.g., blood obtained via blue lumen of right subclavian central catheter) and complete the ordering process.
8. Identify the specimen source and/or specific site correctly so that proper processing methods and culture media will be selected by the laboratory personnel.
9. Deliver the specimen promptly to the laboratory. Delay in transport may compromise the specimen.

SUBCUTANEOUS AND SKIN SPECIMEN:

- A. Superficial Wound (bacterial)
 1. Syringe **aspiration** is preferable to swab collection.
 2. Disinfect the surface of the wound with 70% alcohol followed by povidone-iodine or povidone-iodine alone. Allow the skin disinfectant to dry prior to collection the specimen. Remove iodine with alcohol after procedure to prevent irritation.

3. Using a 3 – 5 ml syringe with a small gauge needle, a physician will aspirate the deepest portion of the lesion. If a vesicle is present, collect both fluid and cells from the base of the lesion.
4. If the initial aspiration fails to obtain material, inject sterile, preservative-free saline subcutaneously then repeat aspiration if necessary.
5. If no material is obtained, rinse needle and syringe with broth by drawing the culture medium through the needle into the syringe.

WOUNDS, ASPIRATES, AND TISSUE SPECIMEN:

A. Deep Wounds or Abscesses:

1. Disinfect the surface with 70% alcohol and a povidone-iodine solution. Remove iodine with alcohol after procedure to prevent irritation.
2. Aspirate the deepest part of the lesion, avoiding contamination by the wound surface. If collection is done at surgery, a portion of the abscess wall should also be sent for culture.

B. Punch Biopsy:

1. Disinfect the skin surface with 70% alcohol and then with a povidone-iodine solution. Remove iodine with alcohol to prevent irritation.
2. Collect 3 – 4 mm sample with a dermal punch.
3. Submit for culture in a sterile container without formalin.
4. Place specimen onto a sterile gauze pad moistened with preservative-free saline in order to keep the specimen from drying.

C. Soft Tissue Aspirate

1. Disinfect the skin surface with 70% alcohol and then with a povidone-iodine solution. Remove tincture of iodine with alcohol to prevent irritation.
2. Aspirate the deepest portion of the lesion or sinus tract. Be careful to avoid contamination by the wound surface.

Appendix 5: 2014 Joslin Clinical Guideline for Adults with Diabetes

Diabetes Mellitus – Diagnostic Criteria (Non-Pregnant Adults)

Random plasma glucose >200 mg/dl and symptoms of diabetes (polyuria, polydipsia, ketoacidosis, or unexplained weight loss)

OR

Fasting plasma glucose (FPG)* >126 mg/dl

OR

Results of a 2-hour 75-g Oral Glucose Tolerance Test (OGTT)* >200 mg/dl

OR

Glycated Hemoglobin (A1C)>6.5%**

*These tests should be confirmed by a repeat test, on a different day, unless unequivocally high

** Only an A1C test that has been referenced to an accepted laboratory method (standardized) should be utilized for diagnostic purposes

---

## 1 Introduction

This document provides details of the statistical analysis plan (SAP) for the C.R. Bard, Inc. protocol DVL-HE-017. An interim analysis will be performed as soon as all subjects have reached 45 days follow-up or have withdrawn from the study earlier. The statistical methods described here are based on the analyses proposed in the Final Protocol issued on **March 23, 2016, Version 4.0**.

All data processing, summarization, and analyses will be performed using Statistical Analysis System (SAS), Version 9.4 software package.

## 2 Study Objective and Endpoints

### 2.1 Study Objective

The objective of this study is to collect additional data on safety, performance and effectiveness of Phasix™ ST in subjects receiving laparoscopic ventral or incisional hernia repair at high risk for SSO. Subjects at high risk are defined as having 1 or more of the following co-morbid conditions: body mass index (BMI) between 30-40 kg/m^2, inclusive, active smokers, chronic obstructive pulmonary disease (COPD), diabetes, immuno-suppression, coronary artery disease, chronic corticosteroid use, low pre-operative serum albumin, advanced age, or renal insufficiency. The study end points are described below.

### 2.2 Study Endpoints

#### 2.2.1 Primary Endpoint

The Primary endpoint is Surgical Site Occurrence (defined as one of the following complications requiring intervention: surgical site infection, seroma, hematoma, wound dehiscence, skin necrosis, mesh infection and fistulas) within 45-days post-implantation.

#### 2.2.2 Secondary Endpoints

1. Surgical Site Occurrence (SSO) (defined as one of the following complications requiring intervention: surgical site infection, seroma, hematoma, wound dehiscence, skin necrosis, mesh infection and fistulas) > 45-days post-implantation follow-up assessment
2. Hernia Recurrence Rate will be assessed by physical examination at each study visit through 24-months. A recurrent hernia will be defined as any hernia identified or confirmed by the investigator, during any study follow-up visit, within 5 cm of the hernia repaired in the study procedure.
3. Surgical Pain Scale - Visual Analog Scale (VAS)
4. Device-related adverse event incidence
5. Rate of reoperation due to the index hernia repair
6. Quality of life assessments (Carolinas Comfort Scale® and SF-12v2®)
7. Surgical procedure time as measured from incision to closure (skin to skin)

8. Length of stay in hospital (day of index surgery until day of discharge, LOS)

### **2.3 Overview**

This is a prospective, multi-center, single-arm, open-label study designed to collect additional data on the safety, performance and effectiveness of Phasix™ ST for laparoscopic ventral or incisional hernia repair. Follow-up visits will be conducted at 1, 3, 6, 12, 18, and 24-months following surgery.

### **2.4 Sample Size Consideration**

This study is projected to treat approximately 120 subjects at approximately 16 sites. The sample size of 120 subjects is based on potential adequacy of data to meet the study objectives. It is not based on any statistical consideration.

## **3 Population Sets**

The Intent-to-treat (ITT) population consists of all enrolled subjects who have signed the Informed Consent Form. The modified ITT (mITT) population is defined as those subjects in the ITT population in whom Phasix™ ST Mesh has been implanted. A Per-Protocol (PP) population may be created if there are subjects who have any major protocol deviations. The PP population will consist of any subjects in the mITT population who do not have any major protocol deviations. The protocol deviations that are considered to have a “major” grade will be defined a priori.

All analyses will be primarily based on the mITT population. Analyses of the Primary endpoint may be performed for PP population as well.

## **4 Primary Endpoints**

The primary endpoint is Surgical Site Occurrence (SSO) up to (and including) 45 days post implantation.

### **4.1 Definitions**

The primary endpoint is defined as the rate of Surgical Site Occurrences (SSO) (requiring intervention) within 45 days post-implantation. SSOs are defined in this study as surgical site infection, seroma, hematoma, wound dehiscence, skin necrosis, mesh infection and fistulas.

### **4.2 Statistical Hypothesis**

There is no formal statistical hypothesis for this post-market study. The study will follow high risk patients implanted with the Phasix™ ST for hernia repair for 24 months.

### **4.3 Primary Analysis**

The proportions of subjects with SSO up to 45-days, and 95% confidence intervals of the rate from exact binomial test, will also be reported. Primary analysis is based on mITT population.

Reported start date of the SSO minus the date of the index hernia repair (implantation of the Phasix™ ST) will be used to determine if a SSO occurred within 45 days from index surgery. Any subjects discontinued before 45 days that do not have an SSO are considered as not evaluable and will be excluded from the analysis.

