6.3.3 Assessments

Subjects should report to their respective study site for follow-up visits at the following postoperative times:

- Pregnancy test for WOCBP within 7 days of index surgery
- 1 month: Day 30 ± 7 days
- 3 month: Day 90 ± 30 days
- 6 month: Day 180 ± 30 days
- 12 month: Day 365 ± 60 days
- 18 month: Day 545 ± 60 days
- 24 month: Day 730 ± 60 days

At each study visit, the following procedures will be completed and these data recorded in source documentation and on the eCRF:

- Surgical Pain Scale -VAS
- Carolinas Comfort Scale®
- SF-12®
- Physical exam to check for hernia recurrence and surgical complications.
A recurrent hernia will be defined as any hernia identified or confirmed by the investigator, during any study follow-up visit, within 5 cm of the hernia repaired in the study procedure. Note: If the subject undergoes imaging for any reason and a recurrent hernia is identified, it must be recorded.
- Concomitant pain medication usage (all pain medication will be captured at baseline and all follow-up visits).
- Assessment of AEs/complications

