6.5 Withdrawal and/or Early Termination

Subjects will be informed that they have the right to withdraw from the study at any time, without affecting their future care.

Additionally, subjects may be discontinued for reasons including, but not limited to the following:

- Consent is withdrawn
- Lost to follow-up (LTFU)
- Investigator withdrawal of subject
- Other

A subject is considered LTFU if the investigational site personnel are unable to locate the subject despite two documented attempts to notify the subject via telephone and a third attempt by certified mail.

A subject is considered an Early Termination (ET), if discontinuation occurs after successful implant of the study device. The site should attempt to bring the subject back to complete all ET visit study procedures (see Table of Study Events).

A subject who receives a re-operation due to hernia recurrence or has the repair site surgically impacted in any way, may be withdrawn from the study upon discharge from the most recent hospitalization. Site personnel will be responsible for documenting adverse events and other post-procedural complications on the applicable eCRF that the subject may have encountered during the hospitalization and up to 30 days post re-operation.

Once a subject discontinues from the study, the Investigator must complete a Study Completion eCRF and the reason for subject discontinuation must be fully documented.

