#### **4.4 Sensitivity Analysis and Handling of Missing Data**

The proportion of subjects with SSO up to 45-days along with 95% confidence interval will be estimated using the Kaplan-Meier method. Number of subjects with events, number of subjects censored and number of subjects left will also be presented.

The time to first event will be the time from index-procedure to the occurrence of the first event. Subjects who do not have a SSO before 45 days and do not discontinue the study before day 45 will be censored at day 45; subjects who discontinue before day 45 will be censored by their discontinuation day. If subjects discontinue at the surgery day then day 0.5 will be used as censor date. Note, the circumstances may be described separately.

A Kaplan-Meier graph will also be provided showing the survival curves for female and males separately.

Additionally, sensitivity analysis will be performed using PP population (if created).

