### **7.5 Follow-up Period**

The duration of follow-up period after the index surgery is calculated as:

Last day in study – date of the surgery

Last day in study is defined as latest of: discontinuation/completion day, last visit day or, last event (AE or reoperation during the study)occurrence day.

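### The primary SSO proportion drops early leavers only if they had no SSO, so it runs slightly high when dropout is unrelated to SSO and promptly recorded; the planned day-45 Kaplan-Meier estimate should lead

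*SAP*

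**What the plan says.** SAP 4.3 reports the proportion of mITT subjects with an SSO up to day 45, with an exact binomial 95% interval. Its rule for early leavers is: "Any subjects discontinued before 45 days that do not have an SSO are considered as not evaluable and will be excluded from the analysis". A leaver who had an SSO stays in numerator and denominator.

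SAP 4.4 estimates the same proportion by Kaplan-Meier as a sensitivity analysis, without naming the interval type. There, "subjects who discontinue before day 45 will be censored by their discontinuation day". Its rule for censoring at day 45 begins "Subjects who do not have a SSO before 45 days", whereas SAP 4 says "The primary endpoint is Surgical Site Occurrence (SSO) up to (and including) 45 days post implantation".

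Protocol 7.3 also puts the rate first and Kaplan-Meier second, uses available data and does not impute. SAP 6 repeats both analyses by sex. Protocol 7.1 and SAP 4.2 state that there is no formal hypothesis.

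Three further places bear on what a leaving date means. Protocol 6.5 treats a subject as lost only if the site cannot locate the subject "despite two documented attempts to notify the subject via telephone and a third attempt by certified mail". SAP 7.5 treats the discontinuation day and the last visit day as separate dates: "Last day in study is defined as latest of: discontinuation/completion day, last visit day or, last event". Protocol 6.3.3 sets "1 month: Day 30 ± 7 days" and then "3 month: Day 90 ± 30 days", so no scheduled visit falls between day 37 and day 60.

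**The concern.** Whether an early leaver enters the denominator depends on the outcome. Keeping leavers with an SSO is sound. The avoidable step is discarding the event-free days of the others, which removes non-events but no events.

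With no hypothesis to test, the day-45 SSO rate and its interval are the main result, so the choice of lead estimator sets the headline number. The day-45 wording also matters: read literally, an SSO on day 45 counts in SAP 4.3 but is censored in SAP 4.4, so the two analyses would not estimate the same quantity.

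**Working it through.** **Inputs.** The documents give about 120 treated subjects, the two handling rules and the visit windows. They give no SSO rate, dropout rate or recording lag, so those are assumed below. The plan has no figure of its own to reproduce, because the sample size is stated to have no statistical basis.

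**1. Direction, prompt recording.** Let p be the true 45-day SSO risk, d the share leaving before day 45 independently of SSO, and q the average SSO risk accrued before leaving. The SAP 4.3 estimate tends to [(1−d)p + dq] / [(1−d) + dq]. Its excess over p is dq(1−p) / [(1−d) + dq], which is positive whenever d and q exceed 0 and p is below 1.

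With SSO and leaving times uniform over 45 days, q = p/2:
- p = 10%, d = 10%: 0.10 × 0.05 × 0.90 / (0.90 + 0.005) = 0.50 points.
- p = 20%, d = 10%: 0.10 × 0.10 × 0.80 / (0.90 + 0.01) = 0.88 points.

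| True rate | 3% dropout | 5% dropout | 10% dropout |
|---|---|---|---|
| 5% | 0.07 | 0.12 | 0.26 |
| 10% | 0.14 | 0.24 | 0.50 |
| 20% | 0.25 | 0.42 | 0.88 |

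If SSOs cluster early (q = 7.6% at p = 10%, q = 15.1% at p = 20%), the excess at 10% dropout is 0.75 and 1.32 points.

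In simulation with n = 120, 10% dropout and no lag, Kaplan-Meier is centred on the truth. Its root mean squared error (RMSE) is 2.82 points against 2.99 for SAP 4.3 at a true 10%, and 3.74 against 3.96 at 20%.

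**2. Late recording.** Suppose the recorded discontinuation day trails last contact by a fixed lag, and let a = (45 − lag)/45. If SSOs in the lag are unseen, SAP 4.3 tends to p(1−d/2) / [1 − d(a − pa²/2)]. At a 30-day lag a = 1/3, which gives 0.095 / 0.9672 = 9.82%. Kaplan-Meier tends to 1 − exp(−∫ observed SSO density ÷ share at risk). Large-sample values (%) for p = 10%, d = 10%:

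| Lag (days) | SSOs in lag | SAP 4.3 | KM, discontinuation day | KM, last contact |
|---|---|---|---|---|
| 0 | – | 10.50 | 10.00 | 10.00 |
| 14 | unseen | 10.18 | 9.74 | 10.00 |
| 21 | unseen | 10.02 | 9.64 | 10.00 |
| 30 | unseen | 9.82 | 9.56 | 10.00 |
| 14 | reported | 10.43 | 10.00 | 10.26 |
| 21 | reported | 10.37 | 10.00 | 10.36 |
| 30 | reported | 10.26 | 10.00 | 10.44 |

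RMSE at n = 120 for the 30-day lag, in the same column order, is 2.76, 2.73, 2.81 (unseen) and 2.81, 2.74, 2.89 (reported). At 14 and 21 days, too, Kaplan-Meier at the discontinuation day has the lowest RMSE of the three.

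**3. Worked example.** Take 120 implanted, D = 12 SSOs and C = 6 event-free leavers, both evenly spread.
- SAP 4.3: 12/114 = 10.5%, exact interval 5.6 to 17.7%, half-width (17.7 − 5.6)/2 = about 6 points.
- Kaplan-Meier: the product of (1 − 1/number at risk) over the 12 SSOs reduces to (119/120)(116/118)(113/115)(110/112)(107/109)(104/106)(102/103) = 0.8973, so 10.3% (log-log interval 6.0 to 17.4%).
- Bounds: D/N = 12/120 = 10.0%; (D+C)/N = 18/120 = 15.0%.
- Informative dropout: if the six had a 30% later SSO risk, the rate is (12 + 1.8)/120 = 11.5%, above both estimates. SAP 4.3 breaks even where (12 + 6q)/120 = 12/114, that is q = 10.5%, with q here the later SSO risk of the six.
- Day 45: the last SSO contributes the factor 102/103. If it falls on day 45 and is counted, Kaplan-Meier is 10.3%. If it is censored, the product stops at 0.9061 and Kaplan-Meier is 9.4%.

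**The case against.** The strongest reply is that nothing is missing. Kaplan-Meier will be reported beside the proportion, SAP 4.3 follows the order in Protocol 7.3, and a small overstatement of a safety rate errs on the cautious side. That is right about importance. It does not defend the exclusion: Kaplan-Meier imputes no outcomes and uses more of the available data.

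The second reply also has force. If SSOs in a recording lag go unseen, Kaplan-Meier as written runs low, and at lags of 14 days or more its mean is further from the truth than that of SAP 4.3 (9.74% against 10.18% at 14 days). Leading with it is therefore not less biased in every setting, although its RMSE was lower in each setting checked.

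A reader might infer that the lead analysis should instead censor at last contact. The documents do not settle this. Protocol 6.5 says when a subject counts as lost, not which date is entered as the discontinuation day, and SAP 7.5 is a formula for follow-up duration, so a lag is possible but inferred. Protocol 6.5 also asks sites to attempt an early-termination visit, and SAP 4.3 dates SSOs by reported start, so a later contact can recover events in the visit gap. If such events are still reported, censoring at last contact handles leavers by outcome again and, at a 30-day lag, is the furthest of the three from the truth (10.44%).

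On day 45, SAP 4.4 opens by describing the proportion up to 45 days, so the literal reading may be unintended. The conflict with SAP 4 remains in the text.

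**Conclusion.** The point holds as a low-cost improvement to consider. The SAP 4.3 exclusion depends on outcome. It gives a slight upward bias if dropout is unrelated to SSO and recorded leaving dates are close to last known SSO status: about 0.5 points at a true 10% and 0.9 at 20%, with an assumed 10% dropout and uniform timing. Interval coverage is not a concern: in simulations at 5 and 10% dropout it was 95.6 to 97.0% for the exact interval and 94.5 to 96.8% for log-log Kaplan-Meier.

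Two stronger readings are not supported. One is that the headline rate is always overstated. When both use the same leaving dates, SAP 4.3 was never below Kaplan-Meier in simulation, but that is an ordering of two estimates, not a comparison with the truth. With a long lag and unseen SSOs both fall below it, and a subject last seen at the one-month visit and recorded as lost after day 45 counts as SSO-free in both. The other is that Kaplan-Meier cures informative dropout. It does not, which is why the bounds are needed.

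The day-45 wording conflict stands whichever estimate leads; in the example it is worth 0.9 points.

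**What to change.** 1. Make the day-45 Kaplan-Meier estimate on all mITT subjects, as planned in SAP 4.4, the lead estimate. Name the interval type, for example log-log, with the exact binomial interval as fallback when a group has no SSO.
2. Reword SAP 4.4 so that an SSO on day 45 is an event, matching SAP 4.
3. Keep the SAP 4.3 proportion with its exact interval as sensitivity. Report the number excluded and the bounds D/N and (D+C)/N.
4. Add Kaplan-Meier censored at last known SSO status as a further sensitivity analysis. Apply one rule to leavers and to continuing subjects not seen after day 45, and let a later contact that covers day 45 count as known to day 45. The second group matters for the interim analysis in SAP 1, which can run before many three-month visits.
5. Use the same order for the by-sex analysis in SAP 6 and align Protocol 7.3.

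The cost is a reordering of two planned analyses, one derived date from visit, unscheduled-visit and adverse event records, and a few wording changes. The downsides are that the headline interval is no longer exact binomial, a zero-event fallback must be specified, and the protocol text must change.
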